2. BACKGROUND AND RATIONALE

2.1 Background – Primary Objective (1)

Preterm infants experience up to 14 painful procedures per day during their first 2 weeks of life²⁶ and neonatal pain experiences prime adult pain responses.²⁷ In rats, painful events in early life can increase the number or glucocorticoid receptors in the hippocampus which may affect future stress responses.²⁸ Incision of the rat paw in early life has been associated with a greater magnitude and duration of hyperalgesia in adulthood.²⁹ Neonatal injury has also been associated with increased intensity, spatial distribution and duration of ionized calcium-binding adaptor molecule-1-positive microglial reactivity in the dorsal horn of the spine (a sensory region of the spine).²⁹ Anatomical differences in neuronal organization of the sensory active subplate zone have been found in preterms, indicating underlying developmental changes due to painful procedures.³⁰ Furthermore, greater

neonatal procedural pain has been associated with reduced white matter and subcortical gray matter volumes by term gestation³¹ and thinner cortices in the frontal and parietal lobes by age seven.³²

To control for pain, opioids (including morphine and fentanyl), sedatives (benzodiazepines), and sucrose have been widely used in the NICU.^{33,34} However, higher cumulative fentanyl doses in preterm infants correlate with a higher incidence of cerebellar injury and lower cerebellar diameter at term age.³⁵ Midazolam, a benzodiazepine sedative, exposure in preterm infants correlates with abnormal hippocampal growth and altered neurodevelopmental outcomes in cognitive, language, and motor abilities.³⁶ Repeated exposure to sucrose for procedural pain in mouse pups reveal smaller white matter volumes in the corpus callosum, stria terminalis, and fimbria, as well as smaller cortical and subcortical grey matter volumes in hippocampus and cerebellum.³⁷

Music has been presumed to be effective in treating pain by provoking feelings of familiarity and security.¹⁹ Soothing music redirects attention from pain inducers, allows for release of brain endorphins, and reduces stress hormones.³⁸ Music has also been shown to relax muscle tone and release body tension.³⁹ Prior music intervention studies on pain have shown overall positive immediate effects on heart rate, facial expressions, latency to cry, and lower pain scores.^{40,41} However, similar to the MBI studies described previously, weaknesses in prior music research on pain in preterm infants consist of inconsistent study approaches with heterogenous study groups, small sample sizes, and varied interventions with mixed outcomes.^{20,40,42–48}

2.1a Study Rationale – Primary Objective (1)

Thus, we propose a novel approach to study immediate and lasting effects of MBI on pain responses in the preterm infant utilizing the standardized Premature Infant Pain Profile (PIPP) and EEG (Aim 1). With frequent music intervention throughout the NICU hospitalization (6 weeks +/- 1 week), pain responses are likely to adapt and change over time. PIPP and EEG are objective, quantifiable outcomes measures that when performed serially will provide pain response trends revealing the cumulative effects of MBI on pain responses throughout the NICU stay. Evaluation of MBI in preterm infants will provide a deeper understanding of music's influence on behavioral processes of the pain response and offer a low risk treatment alternative to the current pain treatment regimen of opioids, benzodiazepines, and sucrose that are detrimental to neurodevelopment.

2.2 Background – Primary Objective (2)

In 2018, the World Health Organization reported 15 million (>1 in 10) preterm births with rising annual rates. While over 90% of those born at ~30 weeks gestation survive, approximately 50% of these infants suffer from neurodevelopmental impairments that span motor, behavior and academic

performance.¹ By 18 months, preterm infants have lower language skills (15 points) on IQ tests compared to term infants.² The most active period of neurodevelopment occurs from conception to 2 years ("first 1000 days") where the effects of environmental exposures may permanently affect functioning throughout life.^{3,4} Healthy neurodevelopment progresses by a complex scaffolding process whereby intricate neural circuits rely on successful completion of previous stages of development.⁴ In particular, the 3rd trimester of gestation is a critical period of rapid brain growth.^{5–9} Although neurodevelopment continues throughout life, by age 2, the brain has undertaken significant restructuring and many developmental changes cannot occur beyond this sensitive growth period.⁴

Nevertheless, music has the remarkable ability to enhance child neurodevelopment. Auditory listening has been found in 27 week fetuses.¹⁰ Fetal auditory learning discriminates low-pitch sound features such as rhythm of music and prosodic features of speech¹¹ and fetuses perceive high-pitched sounds in a similar manner that adults recognize speech sounds.¹² Infants exposed to music prenatally have been shown to recognize familiar melodies at 4 months old suggesting that early music exposure can form lasting neural representations in the brain.¹³ Preterm music listening has been found to increase immediate sleep duration, enhance physiologic functioning (heart rate and oxygen saturation levels), improve behavioural states and weight gain while decreasing hospital stays and initial weight loss.^{14,15} Early music training is associated with enhanced neural speech processing such as pitch changes in speech sounds¹⁶ syllable duration¹⁷ and improved verbal memory skills.¹⁸ Music-based interventions (MBIs) for infants are low-risk¹⁹, minimallyinvasive, and low-cost,²⁰ and thus, an ideal intervention to trial in the neonatal intensive care unit (NICU). The NICU is a necessary but artificial environment created for the survival of preterm infants. It is imperative to carefully select their exposures in this unique environment which overlaps with the timing of the third trimester of pregnancy, a sensitive growth period in which we can have a great impact on immediate and future neurodevelopment.

2.2a Study Rationale – Primary Objective (2)

Thus, we propose a novel approach to study the effects of a longer duration of repeated MBI (6 weeks) by utilizing objective and reproducible measures of electroencephalography (EEG) and event related potentials (ERPs). EEG captures electrical potential oscillations of the brain which yields valuable

information about brain function.²⁵ EEG trends over time reveal brain maturation in preterm infants. Utilizing EEG is a novel approach to studying the biological mechanisms of MBI effects on preterm infants as EEG is objective, captures real-time brain activity, and tracks overall changes in neurodevelopment (Aim 2). Furthermore, ERPs test recognition memory function and cognitive processing of mother vs stranger's voice and offers another objective measure to further study the early effects of the MBI's biological mechanisms on neurodevelopment of these infants (Aim 2).

Thus, we propose a novel approach to study immediate and lasting effects of MBI on pain responses in the preterm infant utilizing EEG and the standardized Premature Infant Pain Profile (PIPP) (Aim 2). With frequent music intervention throughout the NICU hospitalization (6 weeks), pain responses are likely to adapt and change over time. EEG and PIPP are objective, quantifiable outcomes measures that when performed serially will provide pain response trends revealing the cumulative effects of MBI on pain responses throughout the NICU stay (second clinical primary outcome measure). Evaluation of MBI in preterm infants will provide a deeper understanding of music's influence on behavioral processes of the pain response and offer a low risk treatment alternative to the current pain treatment regimen of opioids, benzodiazepines, and sucrose that are detrimental to neurodevelopment.

Successful completion of studying MBI effects on preterm neurodevelopment using rigorous objective measures of EEG and ERPs provides a deeper understanding of the biological mechanisms underlying music intervention in neurodevelopment and could result in a newly established standard of medical care in the NICU to utilize music intervention in the optimization of preterm neurodevelopment. Evaluation of MBI in preterm pain provides a deeper understanding of music's influence on behavioural processes of pain responses which potentially supports music as a low risk, minimally invasive treatment alternative to the current regimen of opioids, benzodiazepines, and sucrose that have detrimental side effects. Outcomes of this R61 would provide foundational work on music and preterm health which can inform future MBI research in optimizing and tailoring different music based interventions to specific patient populations.

Potential Risks

The planned research procedures include: 1) EEG/ERP, 2) PIPP, and 3) Music based intervention or control. These procedures place participating infants at no more than minimal risk.

EEG/ERP

Risks associated with the EEG and ERP are minimal. The EEG electrode placement via EEG caps could cause minor skin irritation or discomfort. Routine skin care, involving gentle cleaning, will be maintained to prevent these side effects. The ERP data will be gathered using Geodesic Sensor net, which may cause similar mild irritation. The EEG/ERPs will utilize EEG caps and Sensor nets rather than traditional electrodes which further minimizes the risk.

PIPP

The PIPP is an observational tool (pain profile) that doesn't require interaction with the subject. The PIPP is performed when the preterm infant undergoes the heel lance procedure for either the Minnesota Newborn Screen or other required blood tests performed during the same approximate time period within the scheduled protocol timeline. The PIPP should not pose any additional risk to the subject as the heel lance for newborn screening or required blood tests are both standard of care. The PIPP will be performed by two study team members concurrently, with the 2nd person either in-person or virtually through a HIPAA compliant method. This is in order to ensure reliability of data collection. The investigator(s) and study statistician will review any discrepancies for statistical analysis.

Music Based Intervention (MBI)

MBI has been shown to be minimal risk. The MBI in this trial (Iullabies) will be played for the infants using headphones placed 1 cm away from the ears to avoid discomfort. During music vs control intervention, a study staff personnel will be actively monitoring the procedure to ensure that cords from the headphones do not interfere with standard of care. The MP3 player has bluetooth capability and should not interfere with routine care. Noise levels are calibrated before every session. Music amplitude will be at no more than 70 dB, which has been shown to be a safe noise level. NICU and study staff will observe for signs of distress during the music therapy, such as crying or finger splay. If these signs continue for more than five minutes, the music therapy will be stopped for that day's session.

Potential risks regarding confidentiality.

There is a potential risk for breach of confidentiality, which will be minimized by the procedures described in the following section.

3. STUDY DESIGN

Pilot randomized, controlled, double blinded music-based intervention (MBI) trial of preterm newborns born at 30 weeks (+/- 2 week) in Neonatal Intensive Care Unit (NICU)

We propose a R61 project to explore the behavioral processes underlying effects of MBI on pain using the premature infant pain profile (PIPP) and EEG. In preterm infants, PIPP scores scale pain responses with painful procedures and central EEG amplitudes change when time-locked to a painful stimulus. The R61 will also explore biological mechanisms of music based intervention (MBI) on preterm brain maturation and neurodevelopment using electroencephalography (EEG) and event related potentials (ERPs). EEG captures electrical potential oscillations of the brain which yields valuable information about brain function. Serial EEGs can track brain maturation in preterm infants. ERPs quantify electrical brain potentials changes time-locked with a stimulus. ERPs at 43-48 corrected gestational

age test recognition memory function and cognitive processing and offers another objective measure to study the early effects of the MBI's on neurodevelopment. Specific recorded lullabies with simple arpeggiated accompaniment will be played for 6 weeks (+/- 1 week) in a small randomized, blinded, controlled study of 60 recruited medically stable 30 week preterms.

Primary Objective - Aim 1: Characterize differences in preterm pain responses between MBI and controls.

Hypothesis/Outcomes:

• Hypothesis 1: MBI will show improved pain responses, with lower PIPP scores and attenuated central EEG amplitude changes during painful procedures, in comparison to the control cohort.

Primary Objective – Aim 2: Identify differences between MBI and controls in preterm brain maturation and early neurodevelopment.

Hypothesis/Outcomes:

• Hypothesis 2: MBI cohort will show enhanced preterm EEG maturation when compared to controls.

Hypothesis 3: ERPs at 1 month (43-48 weeks) corrected age will show that MBI has a greater impact on early neurodevelopment when compared to controls.

Event Related Potentials

Figure 2: Music Intervention

MBI subjects will receive a total of 1.5 hours of music intervention averaged at 4-5 sessions per week (Figure 2). Music will be alternating: 30 minutes on and 30 minutes off and will be played when the subject is awake to cue pacification and initiate the sleep process. Voice unaccompanied or with single accompanying softly arpeggiated instrument⁶⁶ is best for infants. Lullabies meet these criteria and promote language development due to an emphasis on vowels, rising and falling melodic phrases, and the recognition of soothing sounds. Lullabies will all have consistent tempos, with the melody in higher range sung by female or children as infants hear these pitches best.66 As it is recommended to change song order to increase stimulation, habituation, and neurological development, we will use ten playlists. MP3 players will be loaded in advance with the entire 6 weeks

of music. Within each week, order of the playlists will be randomly assigned and prepared in advance by [name]. MBI will have minimal interference with routine medical care. Study coordinators will monitor for any distress from music: finger splay, grimace, vital sign disturbance, or persistent crying.⁶⁷ If crying lasts longer than 5 minutes, the intervention will be stopped for that day's session. Blinding will be maintained by using identical headphones and MP3 players for all subjects. Headphones will be placed on each side of infant's head such that sound stimuli are received binaurally.⁶⁶ Music amplitude will be no more than 70 dB on Scale C.^{15,66,68}

Daily electronic volume level checks will avoid the need for listening checks of the headphones. Headphones will be placed 1 cm away from the ears to avoid discomfort from headphone compression. The headphones will either play music or silence for the control group.

Figure 4: Every two weeks, 30 hour EEG* recordings will capture two sessions of background frequencies and changes that occur with Session 1) MBI or Control intervention or Session 2) [MBI + pain] or [Control + pain]

4. SELECTION AND ENROLLMENT OF PARTICIPANTS

4.1 Inclusion Criteria

Participants must meet all of the inclusion criteria to participate in this study:

Preterm infant born at 30 weeks (+/- 2 weeks)

Medically stable

4.2 Exclusion Criteria

All candidates meeting any of the exclusion criteria at baseline will be excluded from study participation:

Treatment for major organ system disease

Significant neurological disorder including, but not limited to, abnormal neurological examination, neonatal abstinence syndrome, intraventricular hemorrhage, seizures, meningitis, or congenital brain malformations

Scalp lesions affecting EEG placement

4.3 Study Enrollment Procedures_

Newborns will be recruited from the University of Minnesota Masonic Children's Hospital neonatal intensive care unit (NICU). We will ensure staff in the NICU are aware of the study and post flyers in the NICU to alert neonatology staff to the study's purpose, inclusion criteria, and the pager number needed to contact the study staff regarding potential subjects. The neonatologist will first mention the study to the parents, then ask whether the parents would be willing to further discuss the study with the study investigators. Only parents who express interest in learning about the research study will be approached regarding enrollment of their infant.

The PI and other selected study investigators listed on the IRB will obtain consent. All study investigators who will be obtaining consent will receive training on how to determine eligibility of subjects and how to discuss the study with parents. The study investigator who obtains consent will ensure the parents understand the informed consent process and the requirements of the study. Parents will be informed that they can ask questions about the study at any time and contact information for the study staff will be provided on the consent form.

Once eligibility has been confirmed and consent obtained, subjects will be randomly assigned to the MBI or control treatment cohorts in a 50:50 allocation ratio using randomization tables, stratified by sex and within each stratum use randomly allocated block sizes of 2 and 4, prepared by [name].

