The patient recruitment site will be the University of Minnesota Masonic Children's Hospital neonatal intensive care unit (NICU). Infants born at 30 weeks (+/- 2 weeks) who meet both inclusion and exclusion criteria will be identified by NICU staff. The neonatologist will first mention the study to the parent(s)/guardian(s), then ask whether they would be willing to further discuss the study with the study investigators. Study investigators include: (PI) [name], (Music Therapist) [name], [name], and the two study coordinators. The PI, [name], will oversee the consent process and make the final determination of the eligibility. Only parents/quardians who consent to hearing about the research study will be approached regarding enrollment of their infant. At the time of recruitment, all procedures, risks, benefits, and the option to withdraw from the study at any time will be explained to the parent(s)/guardian(s) of each participant and written, informed consent will be obtained. The voluntary nature of the study will be emphasized. The consent form will provide a description of the overall purpose of the research, the specific details of the protocol, risks and benefits, costs and payments, confidentiality, contact information for the PI, the posting of information on ClinicalTrials.gov, and the ability to withdraw from participation. At least one parent/guardian will sign the consent form on behalf of their infant. Assent will not be obtained because participants are not capable of providing it given their very young age (preterm newborn infants). A copy of the signed consent form will be kept in the study research files and medical records. The parent(s)/guardian(s) of participants will also be given a copy of their signed consent form. Parents will be informed that they can ask questions about the study at any time and contact information for the study staff will be provided on the consent form.

Process for meeting HHS regulatory requirements for parental permission and child assent

This study meets the requirements for 45 CFR 46.404 – Research not involving greater than minimal risk. Therefore, according to 45 CFR 46.408, the permission of one parent or guardian is sufficient for research to be conducted, pending IRB approval.

Screening

Both male and female potential subjects will be recruited from the patient population admitted to the University of Minnesota Masonic Children's Hospital NICU.

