6.2.3 Blinding

Blinding will be maintained by using identical headphones and MP3 players for all subjects. The PI, any personnel involved in collecting the clinical outcomes (e.g., PIPP) or collecting or quantifying EEG outcomes, and the statistician will be blinded. The statistician will be aware of blinded treatment group, so that e.g. safety summaries by blinded treatment group can be prepared for the Data Safety and Monitoring Board (DSMB) closed sessions if it so requests. Should the DSMB request unblinded comparisons, the study team will contract with the University of Minnesota CTSI's Biostatistical Design and Analysis Center (BDAC) for an independent statistician to work with the DSMB using unblinded data.

The unblinded staff includes [name] (music therapist) and [name] (Director of the NICU). [name] will prepare the music players. Both will be unblinded to handle randomization, delivery of interventions, and preparations of unblinded reports to the independent study monitors. They will not be involved with data monitoring, analyses, or outcome assessments.

The study coordinators who are assessing the PIPP will wear earplugs and noise cancelling headphones, which will ensure that s/he cannot hear what is emanating from the infant's headphones. In addition, family members and NICU staff will be reminded frequently to not disclose what they think they hear coming from the infant's headphones.

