9.2 Sample Size and Randomization

The R61 phase is exploratory. Based on the number of eligible infants and assuming 60% of eligible subjects enrollment, we can feasibly enroll 60 infants in 1.5 years.. This sample size is similar to or larger than other MBI studies in infants.^{21,23,68,107}

The clinical measure Premature Infant Pain Profile (PIPP) at 4 weeks is the primary outcome for the R61-phase pilot clinical trial. With expected recruitment of at least 60 preterms, expected 50 completed PIPPs at 4 weeks represents a loss to follow-up of $(60-50)/60 = \sim 17\%$. Such a loss rate is slightly more conservative than previous studies completed in the University of Minnesota NICU (which has had ~15% loss rates). This sample size is similar to or larger than other previous MBI studies in infants.

With 50 completed PIPPs at 4 weeks, for comparing MBI to control (25 per group), there is 80% power to detect a group difference in PIPP of 2.9 and 85% power to detect a group difference in PIPP of 3.1. These calculations assume a between-infant standard deviation of 3.6, estimated from the placebo group of a recent study of sucrose as an analgesic for pain from a standard-of-care heel lance. These calculations were carried out in SAS with the following code:

proc power;

twosamplemeans test=diff meandiff = . stddev = **3.6** npergroup = **25**

```
power = 0.80 0.85
    alpha = 0.05
run;
```

;

The R61 exploratory phase data from primary outcome clinical measure PIPP at 4 weeks will be utilized to assist in planning of the R33 phase. The associations of baseline characteristics (infant, e.g. birthweight, and maternal pregnancy history, etc) may inform the design of the R33 phase. For example, these secondary analyses might indicate that we should stratify randomization in the R33 phase by a dichotomized infant birthweight. These analyses, using linear models or non-parametric alternatives if needed (e.g., measures are highly skewed), will use both intervention groups and we will examine the magnitudes of associations in each group and, if appropriate, in the pooled groups.

Treatment Assignment Procedures

Once eligibility has been confirmed and consent obtained. Randomization will be accomplished through the use of randomization tables, stratified by sex and within each stratum use randomly allocated block sizes of 2 and 4. These will be prepared by the study statistician ([name]).

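### Blocks of 2 and 4 within sex, printed in the protocol, make allocation more guessable than it need be at one NICU whose staff put families forward and may overhear earlier arms

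*Combined protocol and SAP*

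**What the plan says.** Section 4.3 assigns infants 1:1 from tables that are "stratified by sex and within each stratum use randomly allocated block sizes of 2 and 4, prepared by" a named team member. Section 9.2 repeats "randomly allocated block sizes of 2 and 4" and gives the preparation to the study statistician; the Précis also states the sizes. These sections name tables only. They describe no sealed, central or other concealment step.

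There is one recruiting unit: "Newborns will be recruited from the University of Minnesota Masonic Children's Hospital neonatal intensive care unit (NICU"). Under section 6.2.1, infants "who meet both inclusion and exclusion criteria will be identified by NICU staff". Under 4.3, "The neonatologist will first mention the study to the parents, then ask whether the parents would be willing to further discuss the study". The PI, who is blinded, makes the final eligibility determination (6.2.1).

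On what can be heard, section 3 says: "The headphones will either play music or silence for the control group". The headphones sit 1 cm from the ears. Section 6.2.3 gives PIPP assessors earplugs and noise-cancelling headphones. For others on the ward, "family members and NICU staff will be reminded frequently to not disclose what they think they hear coming from the infant's headphones".

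Section 6.2.3 also makes the music therapist and the NICU Director unblinded so that they can handle randomization. It keeps both out of data monitoring, analysis and outcome assessment, but is silent on recruitment. Section 6.2.1 lists the music therapist among the investigators with whom parents discuss the study.

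**The concern.** Small blocks are a weakness when the people who choose whom to put forward can learn earlier assignments. In a block of 2 the second assignment is fixed by the first, so mixing the sizes gives limited protection. The reminder to NICU staff in 6.2.3 concerns disclosure. It does not stop the same staff from using what they think they heard.

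Any selection would act before consent: which family hears of the study and when, or how a borderline infant is judged against the medical-stability criterion. The PI's eligibility decision cannot see infants who were never put forward.

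The Go/NoGo milestones in 9.5 compare arm averages with no covariate adjustment described. About 25 infants per arm are expected at the 4-week PIPP, and a difference of 1 PIPP point at any one of three timepoints meets the threshold. An imbalance in who enters each arm would feed directly into that comparison.

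**Working it through.** **The plan's own figure.** The plan gives no figure for predictability, so the check starts from its power calculation (9.2: SD 3.6, 25 per group, two-sided alpha 0.05). For a difference of 2.9, the noncentrality is 2.9 / (3.6 × √(2/25)) = 2.9 / 1.018 = 2.85 on 48 df, and power is 79.7%. For 3.1 it is 84.7%. The stated 80% and 85% reproduce.

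**Inputs.** 1:1 allocation in blocks of 2 and 4 within sex (4.3, 9.2); 60 infants in 1.5 years (9.2); a target of 6 weeks of sessions (6.2.5). Assumptions: 2 and 4 are equally likely (the weights are not stated), and each sex stratum has 30 infants.

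**Guess rate with full knowledge.** The guesser names whichever arm is behind in the stratum and tosses a coin when the arms are level.
- Block of 2: 1/2 + 1 = 1.5 correct of 2 (75.0%).
- Block of 4: 1/2 + 2/3 + 2/3 + 1 = 17/6 correct of 4 (70.8%).
- Equal mix: mean correct (1.5 + 17/6)/2 = 13/6, mean length 3, so 13/18 = 72.2%.
- If the probability of a block of 2 runs from 0.25 to 0.75, the rate runs from 71.4% to 73.3%.

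**Confidence of the guesses.** This was simulated for strata of 30, with an observer who knows past arms and the possible sizes but not the block boundaries.

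| Sizes | Correct | Certain | At least 75% sure | Mean absolute imbalance (maximum) |
|---|---|---|---|---|
| 2, 4 | 72.0% | 10-11% | 55% | 0.2 (2) |
| 4, 6, 8 | 67.5% | about 2.4% | 36% | 0.5 (4) |

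The certain share for 2 and 4 can be checked by hand. One third of blocks of 4 open with two infants in the same arm, which fixes the third and fourth. Per block that is 0.5 × 1/3 × 2 = 1/3 of an assignment, and dividing by the mean length of 3 gives 11.1% in the long run.

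**Guess rate with partial knowledge.** Same simple guesser, strata of 30.

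| What is known | Sizes 2, 4 | Sizes 4, 6, 8 |
|---|---|---|
| 10% of earlier arms missed | 64% | 62% |
| 25% of earlier arms missed | 59% | 58% |
| Latest same-sex arm unknown | 55% | 59% |

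**Overlap in time.** Same-sex entries come on average every 78/30 = 2.6 weeks. If entry is Poisson, the chance that the previous same-sex infant entered less than 6 weeks before the next is 1 − exp(−6/2.6) = 90%. This covers one infant only, not the full history that 72% needs.

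**Cost in power.** At a 22/28 split, power for 2.9 points is 79.1%, against 79.7% at 25/25.

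**The case against.** The strongest objection is to reading 72% as what bedside staff achieve. It belongs to someone who knows every earlier arm in the stratum, and section 6.2.3 says only that staff may think they hear something. Several provisions limit overhearing: music alternates 30 minutes on and 30 off, so a short silence does not identify a control; sessions average 4-5 a week; the devices are identical; and section 11.3 mentions private hospital rooms. This stands. The figure is a ceiling, and a reader who inferred that the ward is in effect unblinded would go beyond the documents.

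A reader might also infer that the milestone comparison is biased. Nothing supports that. No motive to steer infants is documented, and no calculation links the guess rate to a PIPP difference. The text says that the neonatologist will mention the study, not that the neonatologist has discretion over whether to do so.

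The remedy is also weaker than it looks. Naming the arm that is behind requires no knowledge of block size, so removing the sizes mainly reduces certainty, not the average rate. With full knowledge, larger blocks save about (0.720 − 0.675) × 30 = 1.4 guesses per stratum. With partial knowledge they save less, and they do worse if the latest same-sex arm is unknown. Block size is irrelevant to unblinded staff who handle the allocation. Finally, version 8.0 is dated March 2022, and the documents do not say how many assignments remain.

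What survives is narrow. The design is more predictable than it needs to be, most clearly in the share of certain or near-certain guesses, and reducing this costs almost nothing.

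**Conclusion.** The point holds as a minor, inexpensive improvement. Blocks of 2 and 4 within sex allow up to about 72% correct guesses, with 10-11% certain and 55% held with at least 75% confidence. These figures assume equal weights for the two sizes and complete knowledge of earlier arms in the stratum. The 72% barely depends on the weights but depends strongly on the knowledge: it is 59-64% when 10-25% of arms are missed, against 50% by chance. It measures an opportunity for selection before consent and shows no bias. The sample size calculation is unaffected.

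Separately, the unblinded music therapist's randomization role in 6.2.3 sits uneasily with the listing in 6.2.1 among investigators who discuss the study. No choice of block size addresses that.

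**What to change.** 1. For any unused assignments, regenerate the tables with random block sizes 4, 6 and 8 within each sex, and no blocks of 2.
2. Remove the sizes from the Précis, 4.3 and 9.2.
3. Keep the sizes and tables in a restricted file, away from anyone who identifies or approaches families, and say so in the protocol.
4. Reconcile 6.2.3 with 6.2.1 so that nobody who handles randomization also discusses enrolment with parents.

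Steps 3 and 4 matter at least as much as the block sizes, because they address knowledge of the allocation itself.

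The cost is one regenerated table and a short wording change. Mean imbalance per stratum of 30 rises from about 0.2 to 0.5 infants, and the maximum from 2 to 4. Power stays at 79.1% even at 22/28. Visits, outcomes and sample size do not change. If enrolment is complete, steps 1 to 3 no longer apply; the report should then state the block sizes and who had access to the tables.
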